Subjects will be followed for safety during the trial through scheduled clinic visits and phone calls. Adverse events (AEs), regardless of relationship to study drug, will be collected from the time of consent until 28 days post-dose 2 (i.e., Day 56). SAEs, Medically Attended Adverse Events (MAAEs) and AESIs will be collected from time of consent until EOS. SAEs, AESIs and treatment-related AEs will be followed to resolution or stabilization. For the Phase 2 segment and at selected sites in the Phase 3 segment, solicited local and systemic AEs will be collected for 7 days following each dose using a participant diary.

Subjects will also be monitored for COVID-19.

Please refer to the Schedule of Events (Table 3 and Table 4) for safety assessments to be performed.

Efficacy Assessment (Phase 3 segment only):

Subjects will receive either active investigational product (INO-4800) or placebo (placebo for INO-4800) in a 2-dose regimen administered on Days 0 and 28 intradermally followed immediately by EP. Subjects will be monitored through regularly scheduled clinic visits and phone calls throughout the trial. Subjects will be regularly tested for SARS-CoV-2 infection using serologic testing. If COVID-19 disease is suspected based on symptoms per the case definition or laboratory testing, site personnel will arrange for a clinic visit. Subjects with symptom(s) or a positive SARS-CoV-2 test result will be reviewed by the EAC.

Clinical Trial Population:

Phase 2 segment: Healthy subjects at high risk for SARS-CoV-2 exposure who are 18 years and older.

Phase 3 segment: Subjects at high risk for SARS-CoV-2 exposure including subjects at high risk for severe COVID-19 who are 18 years and older.

Inclusion Criteria: Phase 2 segment

- a. Able to provide informed consent and have signed Informed Consent Form (ICF) prior to screening procedures;
- b. Men and non-pregnant women 18 years of age or older;
- c. Assessed by the Investigator to be healthy based on medical history, vital signs and physical examination performed at Screening;
- d. Able and willing to comply with all study procedures;
- e. Working or residing in an environment with high risk of exposure to SARS-CoV-2 for whom exposure may be relatively prolonged or for whom personal protective equipment (PPE) may be inconsistently used, especially in confined settings:

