	Sc	D	0	Tel #1		Vk 4	Wk 6	Tel #2-6	Wk 18	Tel #7-11	Wk 30	Tel #12-13	Wk 42	Tel #14-16	Wk 56	Illness	Illness
		Davio		14 (±3d)		(±3d)	×	s, 70, 84,)	()	140, 154 ±5d)	1)	238, 266	1)	8 (±5d)	5d)	ent visit ⁱ	ent visit ^m
Tests and assessments	Screen ^a	Pre	Post	Phone call - Day 1	Pre	Post	Day 42 (±5d) ^k	Phone call - Days 56, 7 98, 112 (±5d)	Day 126 (±5d)	Phone calls - Days 140, 168, 182, 196 (±5d)	Day 210 (±5d)	Phone calls - Days 2 (±5d)	Day 294 (±5d)	Phone calls Days 322, 350, 378 (Day 393 (± 5	COVID-19 assessment visit	COVID-19 convalescent visit ^m
Informed Consent	Х																
Inclusion/Exclusion Criteria	Х																
Medical history	Х	Х															
Demographics	Х																
Socio-behavioral Assessment	Х																
Concomitant Medications	Х	Х		Х	Х		Х	Х	Х	Х	Х	Х	Х	Х	Х	Х	Х
Physical Exam ^b	Х	Х			Х		Х		Х		Х		Х		Х	Х	Х
Vital Signs	Х	Х			Х		Х		Х		Х		Х		Х	Xn	Xn
Height and Weight	Х																
HIV Serology		Х															
Pregnancy Test ^c	Х	Х			Х												
INO-4800 or Placebo + EP ^d		Х			Х												
Download EP Data ^e			Х			Х											
Adverse Events ^f	Х	Х	Х	Х	Х	Х	Х	Х	Х	Х	Х	Х	Х	Х	Х	Х	Х
Cellular Samples ^g		Х					Х				Х				Х	Xr	Х
Humoral Samples ^h		Х					Х				Х				Х	Xr	Х
SARS-CoV-2 Serology ⁱ	Х	Х			Х		Х		Х		Х		Х		Х		Х
SARS-CoV-2 RT-PCR (Nasopharyngeal swabs)		х														Xo	
Distribute Diary ^p			Х			Х											
Review/Collect Diary ^q				Х	Х		Х										

a. Screening assessment occurs from -30 days to -1 day of Day 0. Screening and Day 0 visits may be combined if eligibility is able to be confirmed prior to dosing. If so, all assessments for Screening and Day 0 must be performed at the combined visit.

b. Full physical examination only at Screening and Day 393 (or EOS). Targeted physical exam at other indicated visits.

INO-4800 Inovio Pharmaceuticals, Inc.

- c. In women of childbearing potential. Urine pregnancy test at all indicated visits.
- d. Intradermal injection(s) in skin preferably over deltoid region, or alternately over anterolateral quadriceps region, followed by EP at Day 0 and Day 28.
- e. Following administration of INO-4800 or placebo, EP data will be downloaded from the CELLECTRA® 2000 device and provided to Inovio.
- f. AEs to be collected from time of consent to Day 56; SAEs, MAAEs, and AESIs to be collected from time of consent to EOS.

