The subject is then requested to sign and date the ICF. A copy of the signed informed consent documentation must be provided to the subject. The qualified clinical trial personnel will document the process of obtaining informed consent within the source record. Signed ICFs are maintained in the subject's source records and must be accessible for verification at any time. Signing of the ICF begins the 30-day screening period.

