7.2 ADVERSE EVENTS (AES)

Any untoward medical occurrence in a patient or clinical investigation subject administered a pharmaceutical product and which does not necessarily have a causal relationship with this treatment.

An AE can therefore be any unfavorable and unintended sign (including an abnormal laboratory finding, for example), symptom, or disease temporally associated with the use of a medicinal product, whether or not considered related to the medicinal product.

Adverse Events (AEs) include the following:

- Pre- or post-treatment complications that occur as a result of protocol mandated procedure during or after screening (before the administration of clinical trial drug);
- Any pre-existing condition that increases in severity, or changes in nature during or as a consequence of the clinical trial drug administration phase;
- Complications of pregnancy (refer to Section 7.11).

Adverse Events (AEs) do not include the following:

- Medical or surgical procedures (e.g., surgery, endoscopy, tooth extraction, transfusion) performed; however, the condition that leads to the procedure is an AE;
- Pre-existing diseases or conditions or laboratory abnormalities present or detected before the Screening Visit that do not worsen;
- Situations where an untoward medical occurrence has not occurred (e.g., hospitalization for elective surgery, social and/or convenience admissions);
- Overdose without clinical sequelae;
- Any medical condition or clinically significant laboratory abnormality with an onset date before the ICF is signed, is not an AE; it is considered to be pre-existing and will be documented on the medical history CRF;
- Uncomplicated pregnancy;
- An induced elective abortion to terminate a pregnancy without medical reason;
- Confirmed COVID-19 disease.

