8.5.3 SAFETY ANALYSES

8.5.3.1 Adverse Events

All AEs including injection-site reactions will be summarized among the Safety Population by frequency per treatment arm. These frequencies will be presented overall and separately by dose, and will depict overall, by system organ class and by preferred term, the percentage of subjects affected. Additional frequencies will be presented with respect to maximum severity and to strongest relationship to Study Treatment. Multiple occurrences of the same AE will be counted only once following a worst-case approach with respect to severity and relationship to Study Treatment. All serious AEs will also be summarized as above.

The main summary of safety data will be based on events occurring within 30 days of any dose. For this summary, the frequency of preferred term events will be compared between study arms with risk differences and 95% confidence intervals, using the method of Miettinen and Nurminen. As this analysis will use many event categories, and produce many confidence intervals, caution should be exercised when interpreting these confidence intervals. Separate summaries will be based on events occurring within 7 days of any dose and regardless of when they occurred.

The analyses listed above will be performed according to the Phase of the trial. For the Phase 2 segment, the analyses listed above will also be performed according to prior receipt of any non-study prophylactic COVID-19 vaccine. For the Phase 3 segment, the analyses listed above will also be performed according to SARS-CoV-2 serostatus at baseline.

For AE data, partial start dates will be imputed to the date of treatment to conservatively report the event as treatment-emergent, whenever the portion of the date is consistent

INO-4800	COVID19-311
Inovio Pharmaceuticals, Inc.	Clinical Protocol

with that of the study treatment. Otherwise, it will be imputed to the earliest date consistent with the partial date. A completely missing onset date will be imputed as the day of treatment. Partial stop dates will be assumed to be the latest possible day consistent with the partial date. AE duration will be calculated as (Stop Date – Start Date) + 1.

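### Section 8.5.3.1 includes a by-arm AE and SAE summary with no time limit, and because collection starts at consent that summary admits events from before the first dose

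*Protocol*

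**What the plan says.** **Collection.** The synopsis (Safety Assessment) says: "Adverse events (AEs), regardless of relationship to study drug, will be collected from the time of consent until 28 days post-dose 2". On the other categories it says: "SAEs, Medically Attended Adverse Events (MAAEs) and AESIs will be collected from time of consent until EOS". Section 6.2 says: "Signing of the ICF begins the 30-day screening period", and footnote a of the Schedules of Events says: "Screening assessment occurs from -30 days to -1 day of Day 0". Footnote a of Table 4 adds: "Screening and Day 0 visits may be combined if eligibility is able to be confirmed prior to dosing"; Section 6.1.1 also allows a same-day visit.

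**What counts as an AE before dosing.** Section 6.1.1.1 has illnesses that first occur after consent recorded as AEs. Section 7.2 includes among AEs: "Pre- or post-treatment complications that occur as a result of protocol mandated procedure during or after screening (before the administration of clinical trial drug".

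**Analysis.** Section 8.1 presents Section 8 as the formal statistical analysis plan. Section 8.5.3.1 opens with: "All AEs including injection-site reactions will be summarized among the Safety Population by frequency per treatment arm". Serious AEs are handled the same way. The main summary uses events within 30 days of any dose and is the only one given between-arm risk differences and confidence intervals. Then: "Separate summaries will be based on events occurring within 7 days of any dose and regardless of when they occurred". The wording is the same in both copies of Section 8.5.3.1 in the document. The treatment-emergent concept appears there once, as the aim of the rule for imputing partial onset dates. It is not defined and restricts no summary.

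**The concern.** An event with onset before the first injection cannot have been caused by the product or the procedure. If it enters a by-arm incidence, it adds the same background to both arms and pulls any true ratio toward 1, which is the unhelpful direction for a safety comparison. The incidences of systemic AEs, SAEs and AESIs are secondary endpoints 1b to 1d.

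The summary without a time limit is not a side table. SAEs, AESIs and MAAEs are followed to Day 393, and those arising more than 30 days after a dose fall outside the dose-anchored summaries. So the summary a reader must use for late serious events is the one that admits pre-dose events.

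The protocol also does not treat this consistently. Sections 8.5.5.2 and 8.5.9.3 separate prior from concomitant medications at Day 0, but no such line is drawn for AEs. The date-imputation rule aims at treatment-emergent reporting, which has little purpose unless some summary is restricted to those events.

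**Working it through.** The plan states no figure on this point, so there is nothing to reproduce. The check sets the collection windows against the summary windows and then sizes the effect.

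**1. Which summaries can contain a pre-dose event**

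| Summary in 8.5.3.1 | Limit stated | Pre-dose events enter? |
|---|---|---|
| Opening sentence, all AEs by arm (SAEs likewise) | none | yes, read literally |
| Main summary | within 30 days of any dose | no on the ordinary reading (after the dose) |
| Separate summary | within 7 days of any dose | no on the ordinary reading |
| Separate summary, any time of occurrence | none | yes, read literally |

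**2. Largest pre-dose share of collection time**

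Inputs: up to 30 days from consent to Day 0 (Section 6.2; Schedule of Events, footnote a); AE collection to Day 56; SAE/AESI/MAAE collection to Day 393.

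- All AEs: 30/(30 + 56) = 30/86 = 35%. With 14 days of screening: 14/70 = 20%.
- SAEs, AESIs, MAAEs: 30/(30 + 393) = 30/423 = 7%. With 14 days: 14/407 = 3%.
- Combined Screening and Day 0 visit: 0%.

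**3. Effect on late serious events (rates assumed)**

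Assume post-dose incidence to Day 393 of 3.0% on INO-4800 and 2.0% on placebo, a constant background rate equal to placebo's, and 30 pre-dose days for every subject.

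- Pre-dose addition in each arm: 2.0% × 30/393 = 0.15%.
- Ratio: (3.0 + 0.15)/(2.0 + 0.15) = 3.15/2.15, about 1.46, against 3.0/2.0 = 1.50.
- Difference: 3.15 − 2.15 = 1.0 point, unchanged in this additive approximation.

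**4. Effect on all AEs to Day 56 (rates assumed)**

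Pre-dose probability in both arms: q = 1 − (1 − p_placebo)^(d/56), with d the pre-dose days. Reported rate: 1 − (1 − p)(1 − q).

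For 10% placebo, 15% INO-4800 and d = 30:

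- q = 1 − 0.90^(30/56) = 5.49%.
- Placebo: 1 − 0.90 × 0.9451 = 14.94%. INO-4800: 1 − 0.85 × 0.9451 = 19.66%.
- Difference 4.7 points (5.0 without pre-dose events); ratio 1.32 (1.50 without).

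With d = 7 and d = 14 the ratio is 1.44 and 1.40, and the difference is 4.9 points in both. Across placebo/vaccine rates from 5%/7.5% to 20%/30% with d = 30, the difference goes from 2.5 to 2.4 points at the low end and from 10.0 to 8.9 at the high end. The ratio falls to 1.31–1.32.

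**5. Balance between arms**

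Randomization is on Day 0 before dosing (Section 6.1.2.1), so pre-dose events precede allocation and have the same expected frequency in both arms.

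**The case against.** **Collection from consent is not an error.** This is right. The gap is in Section 8.5.3.1 alone.

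**The main comparison is dose-anchored.** A reader might infer that pre-vaccination events contaminate the safety rates generally, including the main table, where 30 of 88 days (34%) would be pre-dose if the 30-day window ran both ways. The documents do not support that. Within 30 days of a dose ordinarily means after it, and where the protocol means both directions, as for other vaccines in Section 6.4.7, it says so. What remains is a wording risk: Section 8.5.3.1 gives no direction.

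**The intent is post-dose.** The imputation rule points that way. But a stated intent in a date rule does not restrict a summary whose own text removes the time limit.

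**The harm shows on a ratio, and the planned comparison is a risk difference.** This largely stands. The difference moves little, and the unrestricted summary has no planned between-arm comparison. The reported incidence in each arm is still too high.

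**A reader might apply the Day 56 arithmetic to serious events.** Using 2.0% × 30/56 = 1.07% gives (3.0 + 1.07)/(2.0 + 1.07) = 1.33. That is the wrong window for SAEs and AESIs; with Day 393 it is about 1.46.

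**The constant-rate assumption is generous.** Only dosed subjects are in the Safety Population, and the eligibility criteria would keep out some people with an event during screening. Solicited events are collected only after a dose, and reactions at the study injection site cannot precede one. So the 35% and 7% shares are maxima.

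**Conclusion.** The point holds for the summaries without a time limit. Followed as written, Section 8.5.3.1 puts events from between consent and the first dose into each arm's AE and SAE incidence, including the only summary that holds SAEs, AESIs and MAAEs from more than 30 days after a dose.

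The size is modest. For serious events the assumed ratio of 1.50 becomes about 1.46. For all AEs to Day 56 it could fall to about 1.32, but only if every subject had the full 30 days of screening at a constant background rate. No systematic imbalance between arms is expected. The event rates are assumptions, since the documents give none for this purpose. The main 30-day comparison and the 7-day summary stand on their ordinary reading. This is a stated rule that needs correcting, and it does not threaten the main safety comparison.

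**What to change.** In Section 8.5.3.1:

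- Limit all by-arm AE and SAE frequencies, including the summary without a time limit, to events with onset or worsening on or after the first dose. Keep the existing partial-date imputation.
- State that the 7-day and 30-day windows run from a dose forward.
- List events with onset between consent and the first dose separately, outside the arm comparison.

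Leave collection from consent as it is. The cost is a sentence or two and one programming flag; no new data are needed and none are lost.

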1.1 BACKGROUND AND SCIENTIFIC RATIONALE

Given the continued number of cases globally, SARS-CoV-2 infections remain a serious unmet medical concern. Appropriate measures to prevent SARS-CoV-2 infections, including its variants, are not yet widely available.

1.2 BACKGROUND INFORMATION

In late 2019, a cluster of cases of pneumonia of unknown etiology was reported in Wuhan, Hubei province, China [2-4]. These cases were announced on January 6, 2020 as testing negative for influenza, severe acute respiratory syndrome (SARS), and Middle East respiratory syndrome (MERS). On January 7, 2020 a novel virus was isolated by the Chinese Center for Disease Control and Prevention (CDC) from the throat swab sample of a patient, and the isolate was named "Wuhan-Hu-1." The gene sequence of that isolate was then generated and determined to be of a novel coronavirus [5, 6]. That gene sequence was publicly posted on January 10, and the novel coronavirus was preliminarily named 2019-nCoV. Subsequently, on February 11, 2020, the virus was named SARS-CoV-2 by the International Committee on Taxonomy of Viruses (ICTV) [7, 8], due to its similarity with the original SARS virus. That same day, the World Health Organization (WHO) announced a specific name of the disease, "COVID-19," associated with infection by this novel coronavirus, as based on the novel coronavirus origin and year of first reported cases. The first cluster of human cases identified comprised people who worked, visited, or lived around the local Huanan seafood wholesale market in Wuhan, where live animals and fresh meat and fish were on sale, suggesting that an animal was the source of the novel respiratory virus being transmitted to humans.

Epidemiologic data suggest that droplets expelled during face-to-face exposure during talking, coughing, or sneezing is the most common mode of transmission while contact surface spread remains yet another possible mode of transmission [9].

SARS-CoV-2 infection rapidly emerged as a global threat to public health, joining other coronavirus-related diseases, such as SARS and MERS. COVID-19 was declared a Public Health Emergency of International Concern (PHEIC) by the WHO on January 20, 2020, and was declared a pandemic on March 11, 2020 [10], associated with substantial morbidity and mortality [11]. As of July 25, 2020, a total of nearly 16 million laboratory-confirmed COVID-19 cases have been reported internationally, including over 643,000 deaths [12]. However, given the lack of widespread testing, the true number of cases of COVID-19 is likely far higher than reported. Preliminary results from large U.S.-based seroepidemiological surveys indicate an estimated incidence rate of SARS-CoV-2 infections to be 6 to 24 times that of the number of reported cases of COVID-19 [13].

An article in *JAMA* by Wu and McGoogan [14] provided a summary of a major report by the Chinese Center for Disease Control and Prevention (China CDC) [15]. Of a total of 72,314 case records, 44,672 (62%) were confirmed as SARS-CoV-2 infections based on positive viral nucleic acid test results on throat swabs, 16,186 (22%) as suspected cases based on symptoms and exposures only, 10,567 (15%) as clinically diagnosed based on symptoms, exposures, and presence of lung imaging features consistent with coronavirus pneumonia, and 889 (1%) as asymptomatic cases based on a positive viral nucleic acid

INO-4800	COVID19-311
Inovio Pharmaceuticals, Inc.	Clinical Protocol

test result but lacking typical symptoms including fever, dry cough, and fatigue [16]. The overall case-fatality ratio (CFR) was 2.3% (1023 deaths among 44,672 confirmed cases). No deaths occurred in the group aged 9 years and younger, but cases in those aged 70 to 79 years had an 8.0% CFR and cases in those aged 80 years and older had a 14.8% CFR. The CFR was 49.0% among critical cases. CFR was elevated among those with preexisting comorbid conditions - 10.5% for cardiovascular disease, 7.3% for diabetes, 6.3% for chronic respiratory disease, 6.0% for hypertension, and 5.6% for cancer [16]. These initial reports of the CFR documented the level of seriousness of COVID-19.

Given the novelty of SARS-CoV-2, its rapid spread among humans and its associated morbidity and mortality, there has been an explosion of epidemiological, clinical, virologic, and other scientific data regarding the propagation of effects of this virus emerging from China, the United States, and many other countries. These data have established that 1) SARS-CoV-2 is transmitted person-to-person [17], even from those who are asymptomatic or presymptomatic [18-20], 2) the virus is very infectious, with estimates of the R_0 (Reproductive number) ranging from 1.50 to 6.49, with a mean average of 3.28 and a median average of 2.79 [21], 3) the constellation of symptoms, signs, and an incubation period ranging between 2 and 14 days [22], and 4) the asymptomatic proportion of those infected being substantial, perhaps as high as 80% [17, 23-25]. Further, research has found that the risk of death from COVID-19 increases with age and with serious, comorbid conditions including hypertension, diabetes, cardiovascular disease, obesity, etc.

Finally, although much has been learned very quickly about SARS-CoV-2 and COVID-19, much more is still to be determined. The aforementioned CFR and similar estimates are from crude analyses that have only accounted for moderate to serious cases. Therefore, the true CFR is likely significantly lower. Further, the infection-fatality ratio (IFR), which is the proportion who die among all those infected regardless of any symptomology, is likely still even lower than the CFR, but both the CFR and IFR will not be known with certainty until well-designed and controlled seroepidemiology surveys have been conducted using well-validated antibody assays and thorough questionnaires to obtain symptom history. Also, the presence of natural immunity of those infected who survive and the durability of such natural immunity is to be determined. Thus, the existence and possibility of reinfection and recurrent infection is unknown.

1.2.1 CLINICAL PRESENTATION, TRANSMISSION AND IMMUNE RESPONSE

A study in *The Lancet* by Huang and colleagues [4] reported the epidemiological, clinical, laboratory, and radiological characteristics, as well as treatment and clinical outcomes, of patients with laboratory-confirmed COVID-19 pneumonia. Common symptoms at onset of illness were fever (n=40, 98% of 41 patients), cough (n=31, 76%), and myalgia or fatigue (n=18, 44%); less common symptoms were sputum production (n=11, 28% of 39 patients), headache (n=3, 8% of 38 patients), hemoptysis (n=2, 5% of 39 patients), and diarrhea (n=1, 3% of 38 patients). Dyspnea developed in 22 (55%) of 40 patients (median time from illness onset to dyspnea was 8 days [Interquartile range 5 - 13 days]). Twentysix (63%) of 41 patients had lymphopenia. All 41 patients had pneumonia with abnormal findings on chest CT scan. Complications included acute respiratory distress syndrome (n=12, 29%), RNAaemia (n=6, 15%), acute cardiac injury (n=5, 12%) and secondary infection (n=4, 10%).

Wiersinga et al. summarized the common symptoms of COVID-19 in hospitalized patients as fever (70-90%), dry cough (60-86%), shortness of breath (53-80%), fatigue (38%), myalgias (15-44%), nausea/vomiting or diarrhea (15-39%), headache, weakness (25%) and rhinorrhea (7%). Anosmia and ageusia may be the sole presenting symptom in approximately 3% of individuals with COVID-19. Common laboratory abnormalities

INO-4800	COVID19-311
Inovio Pharmaceuticals, Inc.	Clinical Protocol

include lymphopenia (83%), elevated inflammatory markers (e.g., erythrocyte sedimentation rate, C-reactive protein, ferritin, tumor necrosis factor-alpha, IL-1, IL-6) and abnormal coagulation parameters (e.g., prolonged prothrombin time, thrombocytopenia, elevated D-dimer and low fibrinogen). Common radiographic findings include bilateral, lower lobe infiltrates on chest radiographic imaging and bilateral, peripheral, lower-lobe ground-glass opacities and/or consolidation on chest computed tomographic imaging [9].

Transmission of SARS-CoV-2 occurred mainly after days of illness [26] and was associated with modest viral loads in the respiratory tract early in the illness, with viral loads peaking approximately 10 days after symptom onset [27]. Higher viral loads were detected soon after symptom onset, with higher viral loads detected in the nose than in the throat. Analysis of these samples suggested that the viral nucleic acid shedding pattern of patients infected with SARS-CoV-2 resembles that of patients with influenza [28] and appears different from that seen in patients infected with SARS-CoV [27]. The viral load that was detected in the asymptomatic patient was similar to that in the symptomatic patients, which suggests the transmission potential of asymptomatic or minimally symptomatic patients [11]. The SARS-CoV-2 transmission time window from COVID-19 patients is perhaps 2 days before symptom onset up to 37 days after symptom onset [20]. It is estimated that 48% to 62% of transmission may occur via presymptomatic carriers [9].

Antibody responses to SARS-CoV-2 can be detected in most infected individuals 10-15 days following the onset of COVID-19 symptoms. Seow et al. observed seroconversion in >95% with neutralizing antibody responses when sampled beyond 8 days after onset of symptoms [29]. However, declining neutralizing antibody titers were observed during the follow-up period. Long, et al, when following 37 asymptomatic individuals and 37 symptomatic patients into the early convalescent phase, observed that the IgG levels in 93.3% of the asymptomatic group and 96.8% of the symptomatic group declined during the early convalescent phase [30]. T cells play a critical role in antiviral immunity but their numbers and functional state in SARS-CoV-2 infected patients remain largely unclear. Diao and colleagues performed a retrospective review of total T cell counts, and CD4⁺ and CD8⁺ T cell subsets based on inpatient data from 522 patients with laboratory-confirmed SARS-CoV-2 infection and 40 healthy controls in Wuhan from December 2019 to January 2020. T cell numbers including total T cells, CD4+ and CD8+ T cells in the severe and critical disease groups as well as those who died were significantly lower than in the mild/moderate disease group. Most importantly, the numbers of total T cells, CD8+ T cells and CD4+ T cells in severe COVID-19 cases, including those who died, were lower suggesting that there is a profound T cell loss in COVID-19 disease. Counts of total T cells, CD8⁺ T cells or CD4⁺ T cells were negatively correlated with patient survival [31].

It is quite likely that CD4+ T cell, CD8+ T cell, and neutralizing antibody all contribute to clearance of the acute infection. There is an ongoing need to understand the magnitude and composition of the human CD4+ and CD8+ T cell responses to SARS-CoV-2. If natural infection with SARS-CoV-2 elicits potent CD4+ and CD8+ T cell responses commonly associated with protective antiviral immunity, COVID-19 is a strong candidate for rapid vaccine development [32].

